**Table 7 Progression-Free Survival**

Situation	Date of Progression or Censoring	Outcome
No baseline tumor assessments	Date of first dose	Censored

Situation	Date of Progression or Censoring	Outcome
Progression documented between scheduled visits	Date of last radiological assessment of measured lesions (if progression is based on increase in sum of measured lesions)	Progressed
Symptomatic deterioration before first PD assessment	Date of Symptomatic deterioration	Progressed
Symptomatic deterioration between adequate assessment visits	Date of Symptomatic deterioration	Progressed
Symptomatic deterioration after two or more missed visit	Date of last tumor assessment	Censored
Death before first scheduled assessment	Date of death	Progressed
Death between adequately scheduled assessment visits	Date of death	Progressed
Death or progression after two or more missed visit	Date of last tumor assessment	Censored
New anti-cancer therapy or radiotherapy or surgery at a lesion site prior to confirmed progression (or death)	Date of last tumor assessment where the patient was documented as progression free prior to the intervention	Censored
No progression or death	Date of last tumor assessment	Censored

Summary of PFS including median, 95% CI, 25th and 75th percentiles, range, PFS rate at 3-month, 6-month, 9-month and 12-month will be estimated using the Kaplan-Meier method. The corresponding 95% CI for median will be calculated using the Brookmeyer and Crowley method. The Kaplan-Meier curve and swimmer plot will be displayed.

PFS analysis for the following subgroups will be presented:

- Relapsed/Refractory Patients
- Treatment Naïve Patients
- MR Patients
- MR and Abscopal Decrease Patients

PFS data will be presented in a data listing.

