### 5.6.4 Progression-free Survival (PFS)

PFS is defined as time from date of first study treatment to date of first disease progression by irRC criteria, symptomatic deterioration, or death due to any cause, whichever occurs first. Progression-free survival (PFS) in months is calculated as: (date of first progression, symptomatic deterioration, or death (any reason) – date of first dose +1)/30.4375. The irRC modification requires a PD confirmation no less than 4 weeks from first documentation of progressive Disease (PD); once confirmed, the date of progression is defined as date of the first PD. In case of unconfirmed PD followed by symptomatic deterioration, the date of unconfirmed PD will be the date of progression. Patients without progression, symptomatic deterioration, or death are censored at the date of the last tumor assessment. If a patient begins a new anti-cancer therapy or has radiotherapy or surgery at a lesion site prior to confirmed progression (or death), the patient will be censored at the last assessment where the patient is documented as progression free prior to the intervention. Patients with two or more missing response assessments prior to a visit with progression (or death) will be censored at the last visit where the patient is documented to be progression free. Patients without disease assessment post-baseline will be censored at the first dose date. Table 7 below provides further details on how date of PFS event and date of PFS censoring are assigned.

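### SAP 5.6.4 and its Table 7 can give the same progression two PFS event dates: a conflict when unconfirmed PD is followed by deterioration, an ambiguity for confirmed irPD

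*SAP*

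**What the plan says.** The text of SAP 5.6.4 sets two dating rules for progression. For confirmed progression: "The irRC modification requires a PD confirmation no less than 4 weeks from first documentation of progressive Disease (PD"; and "once confirmed, the date of progression is defined as date of the first PD". For progression that is never confirmed: "In case of unconfirmed PD followed by symptomatic deterioration, the date of unconfirmed PD will be the date of progression".

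The text then hands over to the table: "Table 7 below provides further details on how date of PFS event and date of PFS censoring are assigned". Table 7 has no row that matches either rule. Two of its rows can catch the same patients:

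- Progression found between scheduled visits counts as an event and is dated "Date of last radiological assessment of measured lesions (if progression is based on increase in sum of measured lesions".
- "Symptomatic deterioration between adequate assessment visits" counts as an event on the date of the deterioration, with no exception for a patient who already had an unconfirmed PD.

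The SAP does not say which prevails when text and table differ. PFS in months is the event date minus "date of first dose +1)/30.4375", and "PFS rate at 3-month, 6-month, 9-month and 12-month will be estimated using the Kaplan-Meier method".

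**The concern.** A programmer has good reason to code the PFS date from Table 7, because the SAP presents it as the detailed specification. Anyone who codes from the text can reach a different date for the same patient. The Kaplan-Meier median and the rates at 3, 6, 9 and 12 months would then depend on which part of the section was followed. Nothing in the SAP would show that a choice had been made.

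The overlap is not far-fetched. In the first year scans are 8 weeks apart, and confirmation needs at least 4 weeks, so a confirming scan done promptly will usually fall between two scheduled scans. Protocol Appendix B requires confirmation only when there is no rapid clinical deterioration, so the plan itself expects some patients to have one PD scan and then deteriorate.

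**Working it through.** The documents give no PFS estimate, event count or power figure, so there is no stated number to reproduce. The check applies the SAP's own formula to the planned scan days.

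**Inputs**
- Months = (event day − first-dose day + 1) / 30.4375 (SAP 5.6.4). The 3- and 6-month rates therefore fall at 3 × 30.4375 = 91.3 and 6 × 30.4375 = 182.6 days.
- Scan days for G100 alone: Day 56, or Day 63 to 77 if a ninth dose is given; then Day 112 and every 8 weeks, so Day 168, 224 and on (protocol 3.2, footnotes b and h).
- Minimum time to confirmation: 28 days (SAP 5.6.4).
- First-dose day: in Parts 1 to 3 radiation starts on Day 0 and G100 on Day 2. Both were tried.

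**Unconfirmed PD, then deterioration.** Take a patient with PD on a scan who deteriorates k days later, before the next scan. The text dates the event at the scan and Table 7 dates it k days later. The shift is k / 30.4375 months, and k has no lower limit:
- k = 1: 1 / 30.4375 = 0.03 month.
- k = 14, scan on Day 168, counted from Day 0: 169 / 30.4375 = 5.55 against 183 / 30.4375 = 6.01 months. From Day 2: 5.49 against 5.95, which does not cross 6 months.

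**Confirmed irPD.** The text dates the event at the first PD. If the last radiological assessment in Table 7 means the confirming scan, the shift is at least 28 / 30.4375 = 0.92 month:

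| First PD → confirming scan | From Day 0 (months) | From Day 2 (months) | Crosses a planned rate? |
|---|---|---|---|
| Day 56 → 84 | 1.87 → 2.79 | 1.81 → 2.73 | No |
| Day 70 → 98 | 2.33 → 3.25 | 2.27 → 3.19 | Yes, 3 months |
| Day 77 → 105 | 2.56 → 3.48 | 2.50 → 3.42 | Yes, 3 months |
| Day 112 → 140 | 3.71 → 4.63 | 3.65 → 4.57 | No |
| Day 168 → 196 | 5.55 → 6.47 | 5.49 → 6.41 | Yes, 6 months |
| Day 336 → 364 | 11.07 → 11.99 | 11.01 → 11.93 | No |

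One caution on Day 77: where the next scan is due on Day 112, Day 105 is the edge of the ±7-day follow-up window (protocol 10.1) and might be counted as the scheduled visit. Day 70 confirmed on Day 98 avoids this. So does Part 4 with nine doses, where the next scan is due on Day 133 to 140 (protocol 3.5, footnote h).

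If the phrase instead means the last imaging date within a single assessment whose scans fall on several days, the shift is only those few days.

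**Size of one crossing.** With 12 patients per Part 2 arm (protocol 14.2), one patient moving across a landmark changes that rate by 1 / 12 = 8.3 percentage points, if nobody in the arm has been censored earlier.

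**The case against.** The best defence concerns confirmed irPD. In SAP 5.6.4 and protocol Appendix B, documentation refers to the first PD finding, and confirmation is a separate later step. On that reading, a PD first seen at a scheduled scan was documented at a scheduled visit, so the between-visits row does not apply to it. The text gives the date, and a table that adds detail does not repeal it. This stands as a tenable reading. It is why the point is an ambiguity here and not a flat contradiction. It does not remove the ambiguity, because the row never mentions confirmation and the last radiological assessment is not defined.

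For unconfirmed PD followed by deterioration, the defence is that the specific text rule should override the general table row. That is the natural reading, but the SAP does not state it, and the patient fits both rules as written.

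It is also fair that little rests on PFS. It is a secondary endpoint, offered together with or as an alternative to time to progression (protocol 5.5), and protocol 14.1 calls all analyses exploratory.

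Three stronger inferences are tempting and not supported:
- That every affected event moves by at least 4 weeks. This holds only for confirmed irPD, and only under the confirming-scan reading.
- That any confirmed PD near a landmark crosses it. Day 56 and Day 112 do not at 28 days. Day 63 confirmed on Day 91 gives 92 / 30.4375 = 3.02 months from Day 0 but 90 / 30.4375 = 2.96 from Day 2.
- That duration of response shifts by the same rule. SAP 5.6.3 borrows only the censoring rule from PFS and does not tie its progression date to Table 7.

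**Conclusion.** The point holds as a minor one. SAP 5.6.4 and Table 7 conflict for unconfirmed PD followed by symptomatic deterioration; the shift equals the gap between scan and deterioration and may be a day or several weeks. For confirmed irPD they are ambiguous. The shift is at least 28 days (0.92 month) if the last radiological assessment is the confirming scan, and only days if it is the last image of one assessment. Under the first reading some planned scan days cross the 3- or 6-month rate whether time runs from Day 0 or Day 2.

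How many patients would be affected cannot be worked out from the documents. No sample size, test, error rate or decision rule changes.

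**What to change.** Amend Table 7 as follows:

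1. Add a row for confirmed irPD, whether first seen at a scheduled or an unscheduled assessment, dated at the first assessment that meets irPD and is later confirmed.
2. Add a row for unconfirmed irPD followed by symptomatic deterioration, dated at that unconfirmed irPD assessment.
3. Limit the existing deterioration rows that count as events to patients with no earlier unconfirmed irPD.
4. In the between-visits row, define the last radiological assessment or remove the phrase.

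Leave the censoring rows for two or more missed visits and for new therapy as they are.

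Do not add a general statement that the text prevails. The text censors patients without a post-baseline disease assessment at first dose, while Table 7 counts a death before the first scheduled assessment as an event on the date of death. A blanket rule could turn such deaths into censored observations in the supportive Safety-population analysis (SAP 5.6).

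The cost is SAP wording and the matching analysis-dataset specification. No new data are needed.

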### 5.6.5 Overall Survival (OS)

Overall Survival (OS) is defined as the time from date of first study treatment to death due to any cause. Overall survival in months is calculated as:  $(\text{date of death} - \text{date of first dose}) + 1) / 30.4375$ . Patients who are alive at the end of study will be censored at the last date the patient is known to be alive or data analysis cutoff date, whichever is earlier.

Summary of OS including median, 95% CI, 25th and 75th percentiles, and range will be estimated using the Kaplan-Meier method. The corresponding 95% CI for median will be calculated using the Brookmeyer and Crowley method. The Kaplan-Meier survival curve will be displayed.

OS data will be presented in a data listing.

## **5.6.6 Time to Response for CR or PR Patients**

Time to Response for CR/PR Patients is defined as time from date of first study treatment to the date of CR or PR response first documented. Time to response in months is calculated as: (date of first CR or PR – date of first dose +1)/30.4375.

Summary of Time to Response including median, 95% CI, 25th and 75th percentiles, and range will be estimated using Kaplan-Meier method. The Kaplan-Meier survival curve and swimmer plot will be displayed.

## **5.6.7 Time to Next Treatment and Duration of All Subsequent Therapies**

Time to next treatment is defined as the time from the date of first study treatment to the start date of subsequent therapy after PD. Patients who did not receive subsequent therapy after PD are censored at the date of last contact or death.

Duration of all subsequent therapies after PD in week is calculated as (date of subsequent therapies last administered – date of subsequent therapies first administered + 1)/7. If one patient has multiple consecutive systemic therapies, the duration will be summarized per patient. If the start and end dates of multiple systemic therapies overlap, then duration = (date of last systemic therapy last administered – date of first systemic therapy first administered + 1)/7.

Summary of time to next treatment including median, 95% CI, 25th and 75th percentiles, and range will be estimated using the Kaplan-Meier method. The corresponding 95% CI for median will be calculated using the Brookmeyer and Crowley method. Descriptive statistics using PROC UNIVARIATE of time to next treatment and duration of all subsequent therapies including only patients with subsequent anti-cancer therapies will also be reported.

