8.4.2 Prohibited Concomitant Therapy

The following treatments will be prohibited during study until the EOS visit or tumor progression:

- Any investigational drug other than G100, rituximab or pembrolizumab if enrolled on that study arm, is prohibited during the study
- Any systemic corticosteroid (including prednisone of any dose) within four weeks of first study treatment and during the study period (Intermittent use of inhaled or topical steroids is acceptable but chronic use or high doses where systemic absorption is expected should be discussed and approved by the Sponsor). For patients receiving pembrolizumab, systemic glucocorticoids may be used to modulate symptoms from an event of suspected immunologic etiology. However, the event should be discussed with the Medical Monitor before continuing therapy.
- Other concurrent immunosuppressive medications such as methotrexate, cyclosporine, azathioprine
- Concomitant chemotherapy, immunotherapy not specified in this protocol, or biologic therapy
- Except as given per protocol regimen, radiotherapy
- Anti-coagulation therapy – due to the increased risk of bleeding at the site of injection. Based on the consensus guidelines from the Cardiovascular and Interventional Radiology Society of Europe, if a patient is to have a superficial lymph node or subcutaneous mass injected, NSAIDs, aspirin, or clopidogrel may be used and do not have to be withheld ([Patel 2012](#); [Patel 2013](#)). For procedures with moderate or significant risk of bleeding, long-acting agents such as aspirin or clopidogrel should be discussed with the Medical Monitor and may need to be discontinued before beginning G100 therapy.
- Live vaccines within 30 days prior to the first dose of study treatment and while participating in the study. Examples of live vaccines include, but are not limited to, the following: measles, mumps, rubella, varicella/zoster, yellow fever, rabies, BCG, and typhoid vaccine. Seasonal influenza vaccines for injection are generally killed virus vaccines and are allowed; however, intranasal influenza vaccines (e.g., FluMist®) are live attenuated vaccines and are not allowed.

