Patients are considered to have irPR or irSD even if new lesions are present, as long as they met the respective thresholds of response as described above. Furthermore, patients are not considered to have irPD if new lesions are present and the tumor burden of all lesions did not increase by $\geq 25\%$. In contrast to irCR, irPR, and irPD, a response of irSD does not require confirmation. It is important to note that irCR, irPR, and irSD include all patients with CR, PR, or SD by WHO criteria as well as those patients that shift to these irRC categories from WHO PD. Patients with irSD, particularly those with slow-declining tumor burden $\geq 25\%$ from baseline at the last tumor assessment, are considered clinically meaningful because they show an objectively measurable reduction in tumor burden without reaching the 50% threshold that defines irPR (it represented an objectively measured reduction not commonly observed in the natural history of advanced cancer patients).

If a patient is classified as having irPD at a post-baseline tumor assessment, then confirmation of irPD by a second scan in the absence of rapid clinical deterioration is required. The definition of confirmation of progression represents an increase in tumor burden $\geq 25\%$ compared with the nadir at two consecutive time points at least 4 weeks apart. It is recommended that this be done at the discretion of the investigator because follow-up with observation alone may not be appropriate for patients with a rapid decline in performance status. Confirmation of irPD allows for the capture of all observed responses using the irRC, as most of these late-responding patients have a trend toward response within 4 weeks after initial irPD. Whereas WHO criteria consider any new measurable lesion to indicate PD, determination of immune-related best overall response (irBOR) is based on changes in total tumor burden from the baseline (nadir, for irPD) tumor assessment, regardless of any initial increase in baseline lesions or the appearance of new lesions.

Immune Design**G100 (GLA-SE) and Pembrolizumab or Rituximab****Protocol IMDZ-G142; Version 04B, November 15, 2018****APPENDIX C: REVISED INTERNATIONAL WORKING GROUP RESPONSE CRITERIA FOR MALIGNANT LYMPHOMAS.**

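### SAP 5.6.7 counts only therapy after progression as a time-to-next-treatment event, so a patient who switches therapy before progression stays in the risk set as untreated

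*SAP*

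**What the plan says.** **TTNT.** SAP 5.6.7 measures time from first study treatment to the start of subsequent therapy given after PD. For everyone else: "Patients who did not receive subsequent therapy after PD are censored at the date of last contact or death". The planned Kaplan-Meier summary is the median with 95% CI, the quartiles and the range. A descriptive summary is added, of "time to next treatment and duration of all subsequent therapies including only patients with subsequent anti-cancer therapies will also be reported". The section does not say whether PD means confirmed or unconfirmed irPD, and it has no rule for therapy started before PD. Protocol 14.3.3 lists TTNT among analyses that may be examined as exploratory.

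**Therapy before progression.** SAP 5.6.4 has a PFS rule for a patient who "begins a new anti-cancer therapy or has radiotherapy or surgery at a lesion site prior to confirmed progression (or death), the patient will be censored", and Table 7 repeats it. Protocol 8.4.2 introduces its list of banned treatments with "The following treatments will be prohibited during study until the EOS visit or tumor progression". After the EOS visit, that list does not bar a switch without progression.

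**PFS.** SAP 5.6.4 also says: "In case of unconfirmed PD followed by symptomatic deterioration, the date of unconfirmed PD will be the date of progression". Table 7 has a row for "Symptomatic deterioration between adequate assessment visits", which is an event dated at the deterioration.

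**The concern.** TTNT is meant to show how long patients go before they need another treatment. Under 5.6.7, a patient who leaves for another therapy without documented progression is recorded as still free of next treatment, possibly for many months after that treatment began. The patient is not censored at the switch but stays in the risk set beyond it. The error runs in one direction and flatters the regimen. The arms are small (12 per group in Part 2, up to 25 in Part 3), so one patient can be visible in the estimate.

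A lesser matter sits in the PFS rules. A patient with an unconfirmed irPD scan who then both deteriorates and starts new therapy meets an event rule and a censoring rule, and the SAP does not say which prevails.

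**Working it through.** The documents give no event count, switch rate, median or power for TTNT or PFS, so there is no stated figure to reproduce. The rules are applied to assumed cases, with the SAP's conversion months = (days + 1)/30.4375.

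**1. One TTNT timeline (assumed).** New therapy starts on day 200 without progression, last contact is day 600, and no therapy follows a later progression.
- SAP 5.6.7: censored at (600 + 1)/30.4375 = 19.7 months.
- Counting any next therapy: event at (200 + 1)/30.4375 = 6.6 months.

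If this patient later progressed and began a further therapy, 5.6.7 would record an event, but at that later date. Either way the recorded time is longer than the true one.

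**2. Effect on the planned statistic, the Kaplan-Meier median (illustration).** Assumptions: time to PD exponential with median 12 months; next therapy exponential with mean 2 months after PD; a share s of patients switches at a uniformly distributed fraction of their time to PD; switchers get no later post-PD therapy; cut-off 36 months. Simulated medians (20,000 patients):

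| s | SAP rule | Any next therapy |
|---|---|---|
| 0% | 14.1 | 14.1 |
| 5% | 15.1 | 13.5 |
| 10% | 16.3 | 13.0 |

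Closed-form check. Let a = ln 2/12 and b = 1/2 per month. For a non-switcher, S(t) = (b·exp(-at) - a·exp(-bt))/(b - a). For a switcher's true start, E(t) = exp(-at) - at·E1(at), where E1 is the exponential integral. The SAP-rule median solves s + (1 - s)S(t) = 0.5, which gives 14.1, 15.1 and 16.2 months. The any-therapy median solves s·E(t) + (1 - s)S(t) = 0.5, which gives 14.1, 13.6 and 13.1. These agree with the simulation to 0.1 month.

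**3. One patient in a small arm (illustration).** All other patients are followed past the landmark, d patients have truly started next therapy by then, and one of the d switched before PD. The SAP plans no landmark rate for TTNT; this only gives a sense of scale.

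| n | d | True rate | Switcher censored | Switcher has later post-PD therapy |
|---|---|---|---|---|
| 12 | 4 | 66.7% | 72.7% to 75.0% | 66.7% or 75.0% |
| 12 | 5 | 58.3% | 63.6% to 66.7% | 58.3% or 66.7% |
| 12 | 6 | 50.0% | 54.5% to 58.3% | 50.0% or 58.3% |

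For d = 6, the true rate is 6/12. Censoring before any other event gives 6/11 = 54.5%. Last contact after the landmark gives 7/12 = 58.3%. A later post-PD therapy before the landmark leaves 6/12, and after it gives 7/12. The shift is therefore 0 to 1/12, or 0 to 8.3 points. With n = 25 the upper limit is 1/25 = 4.0 points. For comparison, the exact 95% interval for 6/12 is 21.1% to 78.9%.

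The 0 lower limit assumes no other censoring. With other patients censored in between, a single small sample can behave irregularly. The upward direction is a statement about the distribution being estimated.

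**4. PFS overlap (assumed timeline).** Last progression-free scan day 112, unconfirmed irPD day 168, deterioration day 180, new therapy day 185.
- 5.6.4, unconfirmed-PD sentence: event at 169/30.4375 = 5.55 months.
- Table 7, deterioration row: event at 181/30.4375 = 5.95 months.
- New-therapy rule: censored at 113/30.4375 = 3.71 months.

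The first-occurring clause in 5.6.4 orders progression, deterioration and death among themselves. It does not rank an event against the new-therapy rule, whose trigger omits deterioration.

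**The case against.** The best defence of 5.6.7 is that it follows the protocol's collection design. Next-treatment history is scheduled in follow-up after progression, and SAP 3.2 ties TTNT to patients who have progressed. Time to post-progression therapy is a coherent, narrower target. That explains the wording. It does not justify leaving a patient in the risk set after next treatment has begun, and the endpoint is labelled simply as time to next treatment. It is also true that subsequent therapies are listed, so early switchers are not hidden, and that the stakes are low.

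A reader might infer three stronger things.
- *That 5.6.7 contradicts itself, because the descriptive summary carries no progression condition.* Both variables in that summary are defined earlier in the same section as post-progression quantities, so a consistent reading exists.
- *That every early switcher raises the estimate.* A switcher with a later post-PD therapy before the landmark leaves it unchanged.
- *That PFS needs an added sensitivity analysis counting unconfirmed irPD followed by new therapy as an event.* Take 8-weekly scans and a 12-month median, so the per-scan risk is p = 1 - 2^(-8/(12 × 4.348)) = 0.101 and true week-48 PFS is (1 - p)^6 = 52.9%. Let q = 20% be the switchers as a share of p, with s = half of them pseudoprogressors. The present rule has per-scan hazard (1 - q(1 - s))p/(1 - qp) and gives 55.8%. The event rule has p(1 + qs) and gives 49.4%. The alternative misses by about as much in the other direction, so it is a preference, not a correction.

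On the PFS overlap, much can be resolved by reading. Deterioration is itself a PFS event, and Protocol Appendix B says "confirmation of irPD by a second scan in the absence of rapid clinical deterioration is required", so deterioration can stand in for confirmation. The clearest gap is an unconfirmed scan, then new therapy, then deterioration.

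**Conclusion.** The TTNT point holds. As written, 5.6.7 keeps a patient who switches before progression at risk as untreated, which leaves TTNT unchanged or biases it upward. Reading the text is enough to establish this. The sizes are not established: the medians of 15.1 versus 13.5 and 16.3 versus 13.0 months rest on assumed switch shares, an assumed 12-month median time to PD, and no later post-PD therapy for switchers. The one-patient shift of 0 to 8.3 points in an arm of 12 is small against the sampling error.

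No primary conclusion, futility rule or sample size depends on TTNT, and there may be no affected patients at all. The change is worth making because the error is directional, avoidable and cheap to remove. The PFS matter is a minor clarification and the main point does not depend on it.

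**What to change.** **In SAP 5.6.7**, define the TTNT event as the start of the first subsequent anti-cancer therapy regardless of PD status, not counting protocol-specified study treatment such as the second G100 course. Use the same definition in the descriptive summary.

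**Minor clarification in SAP 5.6.4 and Table 7.** State which rule applies when symptomatic deterioration and new therapy both follow an unconfirmed irPD scan, for example whichever came first. Align the date of the deterioration event between the text and the table.

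**Cost.** A few sentences and the matching programming specification. No new data should be needed, because the 5.6.4 censoring rule already requires the start date of therapy begun before confirmed progression. The downside for the sponsor is that TTNT may look slightly less favourable.
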